4.2.5.2 Laboratory data

All continuous laboratory parameters will be summarized by absolute value at each visit by treatment group, together with the corresponding changes from baseline. The summary statistics presented will be the minimum, 1st quartile, median, 3rd quartile, maximum, mean and SD. Mean changes from baseline over time will also be plotted by treatment group.

Central (or local) laboratory reference ranges will be used for the identification of individual clinically important abnormalities, and a shift table will be produced for each laboratory parameter to display low, normal, high, and missing values. The shift tables will present baseline and last on-treatment value for each parameter. On-treatment is defined from date of first dose and including visit 14 (week 12).

Shift plots showing each individual subject's laboratory value at baseline and at the last on-treatment value will be produced for each continuous laboratory variable. If any laboratory variables show any unusual features (high or low values or a general shift in the data points) at other time points, then shift plots of these data may be produced. A diagonal line indicating no change, and horizontal and vertical reference lines indicating the limits of the central (or local) laboratory reference ranges will also be displayed on the shift plots.

Data for subjects who have treatment-emergent changes outside predefined criteria will be presented. This data presentation will include all visits for this subset of subjects. A change is treatment-emergent if it occurred during treatment, from the date of first dose of randomised treatment up to and including the follow-up period.

The frequency of treatment-emergent changes outside predefined criteria between baseline and each post-treatment time point will be tabulated

In order to identify potential Hy's Law cases, maximum post baseline TBL will be plotted against maximum post baseline ALT, expressed as multiples of ULN. This plot will be repeated to show maximum post baseline TBL against maximum post baseline AST, expressed as multiples of ULN. These plots will be produced on a log scale and reference lines will be included at 2xULN for TBL and at 3xULN for ALT/AST.

For all subjects who meet the biochemical criteria for Hy's law (potential Hy's Law), a Subject Safety Narrative will be produced, and the relevant laboratory parameters will be tabulated showing all visits for these subjects. Subjects with elevated ALT or AST, and elevated TBL, at any time may be explored further graphically using individual subject profile plots.

Any data outside the laboratory reference ranges will be explicitly noted on the listings that are produced.

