3.4.1 Adverse events

The definitions of adverse events (AEs) and serious adverse events (SAEs) are given in Sections 6.1 and 6.2 of the CSP.

All AEs recorded in the eCRF will be coded according to the terminology of the latest version of the Medical Dictionary for Regulatory Activities (MedDRA).

All adverse events will be listed for each patient and summarised by treatment actually received. Treatment-emergent AEs will be tabulated (number and percentage of patients) by system organ class (SOC), preferred term (PT), intensity and relation to study medication.

Any AE occurring before the start of study treatment will be included in the data listings but will not be included in the summary tables of AEs and excluded from safety analysis set.

If an AE has a missing onset date then unless the stop date of the AE indicates otherwise, this will be considered 'on-treatment'. Similarly, if an AE has a partial onset date, then unless the partial onset date or the stop date indicates otherwise, this will be considered 'on-treatment'.

AE data will be categorized according to their onset date into the following periods:

- AEs starting during pre-treatment (onset date \geq Visit 1 (Week -4) and before the first dose of IP)
- AEs starting during study (onset date \geq the first day of IP and \leq Visit 21 (Week 52))
- AEs starting during ICS + LABA treatment period (onset date \geq the first day of IP and $<$ Visit8 (Week 6))
- AEs starting during ICS taper down period (onset date \geq Visit 8 (Week 6) and $<$ Visit 11 (Week 9))
- AEs starting during remainder of study (onset date \geq Visit 11 (Week 9) \leq Visit 21 (Week 52))

The timing of AEs will be assigned to the period in which they first started. The same during treatment definition will be used for laboratory and physical examination data, where applicable. Note, not all Exacerbations will be recorded as AEs.

Common AEs, AEs with outcome of death, SAE, DAEs and Flu-like AEs will be summarized separately. Flu-like AEs are defined in [Section 4.2.5.1](#).

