3.4.2 Laboratory

Blood and urine samples will be used for determination of clinical chemistry, haematology and urinalysis parameters taken at scheduled time points as specified in Table 1, Section 4 of the CSP. The laboratory parameters to be measured are given in Table 3, Section 5.2.1 of the CSP. Laboratory data will be reported using Système International (SI) units.

Changes in haematology and clinical chemistry variables between baseline and each subsequent scheduled assessment will be calculated.

Absolute values will be compared to the relevant reference range and classified as low (below range), normal (within range or on limits) or high (above range). The central laboratory or local laboratory (for assessments measured at a local laboratory) reference ranges will be used for laboratory variables. All values (absolute and change) falling outside the reference ranges will be flagged.

Urinalysis data will be categorised as negative (0), trace, or positive (+) at each time-point and will be listed only.

For the purposes of haematology and clinical chemistry shift tables, baseline will be defined as the latest non-missing assessment prior to first dose, and during-study is as defined in [Section 3.4.1](#). Shift-tables will not be presented for the specific periods separately, i.e. ICS+LABA treatment period, ICS taper-down period or during the remainder of study. On treatment is defined as from date of first dose and including visit 14 (week 12).

For the liver function tests: Aspartate Aminotransferase (AST), Alanine Aminotransferase (ALT), Alkaline phosphatase (ALP) and total bilirubin (TBL), the multiple of the central or local laboratory upper limit of the normal (ULN) range will be calculated for each data point.

$$\text{Multiple} = \text{Value} / \text{ULN}$$

i.e. if the ALT value was 72 IU/L (ULN 36) then the multiple would be 2.

Patients who meet any of the following criteria at any point during the study will be flagged:

- $\text{AST} \geq 3\text{xULN}$
- $\text{ALT} \geq 3\text{xULN}$
- $\text{TBL} \geq 2\text{xUL}$

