4.2.5.3 Vital signs

All vital signs parameters will be summarized by absolute value at each visit by treatment group, together with the corresponding changes from baseline. The summary statistics presented will be the minimum, 1st quartile, median, 3rd quartile, maximum mean and SD.

AstraZeneca defined reference ranges will be used for the identification of individual abnormalities, and a shift table will be produced for each vital signs parameter to display low, normal, high, and missing values. The shift tables will present baseline and maximum/minimum during treatment value, as applicable for each parameter.

Shift plots showing each individual subject's vital signs value at baseline and at maximum/minimum will be produced for each continuous vital signs parameter.

Data for subjects who have treatment-emergent changes outside the predefined criteria will be presented, using AstraZeneca clinically important change criteria. This data presentation will include all visits for each parameter with treatment-emergent changes for this subset of subjects. A change is treatment-emergent if it occurred on study as defined in [Section 3.4.1](#).

Data collected during the Sentinel visits will not be included as part of the summary statistics calculations or shift plots and will not be flagged, However, all recorded vital signs data will be listed.

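### Laboratory shift tables use only the last on-treatment value, so a blood count that falls and recovers during dosing is tabulated as no shift

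*SAP*

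**What the plan says.** SAP 4.2.5.2 uses laboratory reference ranges to pick out individual abnormalities and provides a shift table (low, normal, high, missing) for each parameter. On its content: "The shift tables will present baseline and last on-treatment value for each parameter". The next sentence sets on-treatment as first dose through Visit 14 (Week 12). The required shift plots for continuous variables also use baseline and the last on-treatment value. Shift plots at other time points are optional and depend on something unusual being noticed.

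Other laboratory outputs are planned:

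- Summaries at each visit by treatment group, including the minimum and quartiles (SAP 4.2.5.2).
- An all-visit presentation for a subset of patients: "Data for subjects who have treatment-emergent changes outside predefined criteria will be presented".
- A table by time point: "The frequency of treatment-emergent changes outside predefined criteria between baseline and each post-treatment time point will be tabulated".
- Flags against the reference ranges (SAP 3.4.2): "All values (absolute and change) falling outside the reference ranges will be flagged".

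For vital signs, SAP 4.2.5.3 makes a different choice: "The shift tables will present baseline and maximum/minimum during treatment value, as applicable for each parameter".

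**The concern.** A last-value shift table answers one question: where did the patient end up at the close of dosing? It does not show whether the patient was ever low during dosing. For a reversible effect, the second question matters more.

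The protocol gives a reason to ask it. Section 1.3 reports that injected TLR9 agonists have in some cases caused haematological effects, and its example is a transient fall in lymphocytes. A fall that recovers is the pattern a last-value table misses.

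The adverse event tables would not necessarily fill the gap. Under Protocol 6.3.6, a worsening in a protocol-mandated laboratory value is reported as an adverse event only if it meets a seriousness criterion or is the reason for stopping the drug. Associated symptoms are reported in their own right, but a symptom-free low count would appear only in the laboratory outputs. At stake is whether the study report gives a plain count, by arm, of patients who had such a fall.

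**Working it through.** No figure in the plan bears on this point, so the check traces one hypothetical patient through each planned output. The patient has a normal lymphocyte count at baseline, one low count at a mid-dosing sample, and a normal count at the last on-treatment sample.

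| Planned output | What it uses | Is the low value visible? | Does it count the patient once, by arm? |
|---|---|---|---|
| Shift table (4.2.5.2) | Baseline and last on-treatment value | No: normal to normal | It counts patients, but this one as unshifted |
| Required shift plot (4.2.5.2) | Same two values | No | No |
| By-visit summary (4.2.5.2) | All values at that visit | Partly, through the minimum and quartiles | No |
| Frequency table (4.2.5.2) | Changes outside predefined criteria, per time point | Yes at that visit, if the criteria cover low values | No |
| All-visit subset presentation (4.2.5.2) | Every visit of patients with such a change | Yes, on the same condition | Not as a table; a reader could count by hand |
| Flags and listings (3.4.2, 4.2.5.2) | Every out-of-range value | Yes | Not as a table; a reader could count by hand |

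**Why the frequency table does not give the patient count.** Its treatment-emergent window opens at first dose, so dosing visits are included. But its counts are per time point. One low value at each of two visits may come from one patient or from two, and the table cannot tell them apart.

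**Whether the SAP uses worst values elsewhere.** It does. Vital-sign shift tables use the extreme during treatment. In the laboratory section itself, the Hy's Law plots use the maximum post-baseline bilirubin and transaminases. SAP 3.1.4 already lets unscheduled results enter a within-period maximum or minimum. No reason is given for keeping the blood-count shift tables on the last value only.

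**Whether the data for a minimum-value table are collected.** They are. Protocol Table 3 lists haemoglobin, platelets and an absolute leukocyte differential, which supplies lymphocytes and neutrophils.

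**Whether the loss can be sized.** It cannot from these documents. That would need a rate of low counts, which is not given, and the number of haematology samples taken during dosing. Protocol Table 4 plans 8 haematology samples per patient over the whole study, but the schedule of events is too broken in the available text to show which of them fall between first dose and Week 12.

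**The case against.** The strongest reply is that the signal is not hidden. The SAP plans by-visit minima by arm, a frequency table of excursions at each time point, all-visit data for every patient with an excursion, and flags on every out-of-range value. SAP 4.1 sorts listings by treatment and patient, so the patient count could be made by hand. Beside these outputs, a last-value shift table is a legitimate descriptive choice, and using extremes for vital signs does not make it an error for laboratory data.

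Patient protection does not rest on this table either. Investigators assess laboratory results as they arrive (Protocol 5.2.1), and the safety board may review unblinded data (Protocol 6.8.1). The link to this drug is indirect: the class effect was reported with injected agents, whereas AZD1419 is inhaled and was undetected in plasma at 23.1 mg, against a maximum of 8 mg here (Protocol 5.4). A minimum-value table also picks up more chance lows.

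Most of this stands, and it sets the weight. It does not remove the gap: finding the patients through listings is not the same as a by-arm table that counts each of them once. The chance lows arise in both arms, so placebo shows how many to expect.

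**Conclusion.** The point holds as a minor reporting improvement. A sampled low count that recovers by the last on-treatment sample is shown as no shift, and no described table counts each patient once per arm for any on-treatment low value. No formal safety test is planned, and no size can be put on the loss from the documents. The conclusion assumes that the table shells add nothing beyond the SAP text. It covers only falls that a sample catches; a fall between samples is invisible under any table.

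Two stronger readings are tempting and are not supported.

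- A reader might infer that transient low counts would be lost from the report. They would not: the other planned outputs show part or all of such a signal. The SAP does not expressly say what the laboratory predefined criteria are, but reference ranges are the natural reading, and naming them is an optional clarification.
- A reader might infer that the shift-table window is open or runs to Week 52, because SAP 3.4.2 describes baseline for these tables as "the latest non-missing assessment prior to first dose, and during-study is as defined in" Section 3.4.1, where the study period extends to Visit 21. But SAP 4.2.5.2, which specifies the tables, uses the last on-treatment value and ends that period at Visit 14, and SAP 3.4.2 gives the same definition of on-treatment. The window is Week 12.

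**What to change.** Keep the last-value shift table. Add one sentence to SAP 4.2.5.2: for lymphocytes, neutrophils, platelets and haemoglobin, a further shift table by treatment group will show baseline against the minimum value from first dose through Visit 14, with unscheduled results included as SAP 3.1.4 allows. Optionally, add a clause saying that the laboratory predefined criteria are the reference ranges, or list them if they are something else.

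The cost is that sentence and a second run of an existing shift-table program, with no new data collection. The downside is more chance lows, because a minimum over several samples is more likely to fall below range than a single value. The table should be read against the placebo column.

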4.2.5.3 Vital signs

All vital signs parameters will be summarized by absolute value at each visit by treatment group, together with the corresponding changes from baseline. The summary statistics presented will be the minimum, 1st quartile, median, 3rd quartile, maximum mean and SD.

AstraZeneca defined reference ranges will be used for the identification of individual abnormalities, and a shift table will be produced for each vital signs parameter to display low, normal, high, and missing values. The shift tables will present baseline and maximum/minimum during treatment value, as applicable for each parameter.

Shift plots showing each individual subject's vital signs value at baseline and at maximum/minimum will be produced for each continuous vital signs parameter.

Data for subjects who have treatment-emergent changes outside the predefined criteria will be presented, using AstraZeneca clinically important change criteria. This data presentation will include all visits for each parameter with treatment-emergent changes for this subset of subjects. A change is treatment-emergent if it occurred on study as defined in [Section 3.4.1](#).

Data collected during the Sentinel visits will not be included as part of the summary statistics calculations or shift plots and will not be flagged, However, all recorded vital signs data will be listed.

4.2.5.4 Diffusing Capacity of the Lung for Carbon Monoxide (DLco)

DLco at each visit for which it is recorded will be summarized by treatment group with descriptive statistics.

4.2.5.5 ECG

The Investigator's assessment of the 12-lead ECG (normal or abnormal) will be listed for all subjects, along with detailing whether any abnormalities were clinically significant or not.

A shift table will be produced showing the change between baseline and the end of study assessment.

Absolute values and change from baseline for ECG parameters RR, PR, QRS and heart rate reported by the central ECG laboratory will be summarized by visit. The reference ranges are presented in [Table 4](#).

Table 4 ECG reference ranges

| Parameter | Standard Units | Lower Limit | Upper Limit |
|------------------|-----------------------|--------------------|--------------------|
| ECG Heart rate | Beats/min | <60 | >100 |
| RR interval | ms | <60 | >100 |
| PR interval | ms | <120 | >200 |
| QRS duration | ms | <60 | >120 |

4.2.5.6 Physical examination

Shift tables (normal, abnormal (same as baseline, new or aggravated)) of baseline versus last on-treatment observation will be generated, presenting the assessment for each component of the complete physical examination separately. Listings of abnormal results will be produced.

4.2.5.7 Composite endpoint for exacerbations (CompEx)

Time to (first) CompEx event, for each of the five variants of CompEx, will be compared between AZD1419 and Placebo using a Cox proportional hazard model adjusting for treatment group. The hypothesis test will be 2-sided, with alpha=0.05.

Data will be visualized using Kaplan-Meier plots.

The proportion of subject's with CompEx events will be compared between treatments using a log-binomial regression model. Treatment group will be included as a factor in the model. The back-transformed estimated treatment effect (i.e. the ratio of proportions, AZD1419 over placebo, will be presented with 2-sided 95% confidence interval and p-value (2-sided alternative). The model will be fitted using the SAS[®] procedure PROC GLIMMIX as described in [Section 4.2.4.1](#).

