Slopes are computed over 5-day intervals with the last day of the interval being the start day of the event. If there is less than 2 days with available data in an interval, slope is set to missing and the condition is not fulfilled. Thresholds are computed for 2-day intervals with the first day of the interval being the start day of the event.

Threshold diary events are defined as starting at the earliest on the start day of treatment (Day 1), with event on Days 1-2, and at the latest ending on Day 364 (event on Days 364-365).

Slope diary events (start day of treatment = Day1) are defined as starting at the earliest on Day 5 (with event on Days 1-5) and ending latest on Day 365 (with event on Days 361-365). However, if slope diary events are calculated for those days where at least one variable fulfills a threshold criterion, the last possible day for a slope diary event will be Day 364.

For subjects prematurely discontinuing, the above definitions will be amended for actual end day of treatment and actual start day of post-treatment.

Events are searched for up to the last day with entry in the diary cards. Missing values indicate no event. Missing diary data will not be imputed. If diary card entries stop prematurely (before the last day in the study) or if the patient lacks data during the period, the patient is to be censored as having no event at the last day in the period. This will be either the last day with recordings in the diary or the last day the patient was assessed for severe asthma exacerbation.

The outcome variables for CompEx events will be as follows:

- Time to first CompEx event during the 52-weeks following randomisation, for each of CompEx PR, PS, PA, PRS and PRSA
- Proportion of patients with a CompEx event during the 52-weeks following randomisation, for each of CompEx PR, PS,PA, PRS and PRSA

Table 3 Definition of diary events evaluated as possible building blocks for CompEx

| Diary event | Variables | Definition |
|-------------|---|--|
| PR | P - PEF morning/evening R - Reliever morning/evening | 2/2 days above threshold on PEF (morning or evening) and reliever (morning or evening), or 2/2 days above threshold on 1/4 variables + 4/4 slopes |
| PS | P - PEF morning/evening S - Symptoms morning/evening | 2/2 days above threshold on PEF (morning or evening) and symptoms (morning or evening), or 2/2 days above threshold on 1/4 variables + 4/4 slopes |

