4.2.4.1 Loss of asthma control as group proportions

The proportion of patients with loss of asthma control will be compared between the two treatment groups at each clinical visit, using a generalized linear model based on a generalized estimating equations (GEE) approach, with occurrence of any loss of control as a binary outcome variable. Treatment group and visit will be included as factors in the model. The covariates for inclusion in the statistical model are described in Section 4.2.1. If a patient had

a ‘loss of asthma control’ event at one visit, the subsequent visits information should be removed. Each patient can only be counted once towards ‘loss of asthma control’.

This analysis will be carried out using a log-binomial regression model using PROC GLIMMIX in SAS with a random subject effect. The estimated treatment effect (i.e. the rate ratio of AZD1419 versus placebo), corresponding 95% confidence interval (CI), and two-sided p-value for the rate ratio will be presented.

In the case that If the GEE model fails to converge, due to the estimation method not being Restricted Maximum Likelihood (REML), then only the Mixed Model will be explored. The variance-covariance will be assumed to be unstructured. other options will be explored e.g. using the PROC GLIMMIX procedure in SAS. For PROC GLIMMIX, initially this will be fitted with a random statement fitting a random intercept and a Laplace approximation for maximum likelihood estimation. Again, to facilitate convergence, one or more of the covariates could be removed leaving the basic model. In case this model also fails to converge, the random statement will be removed which will result in a conventional logistic regression model being fitted.

The assumptions underlying the statistical model will be explored. If assumptions do not hold, then alternative strategies will be considered.

Summary statistics will also be presented for each treatment group at each visit.

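### The CompEx proportion model is cross-referenced to a by-visit model whose random subject effect cannot be estimated from one record per patient and whose last fallback is an odds ratio

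*SAP*

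**What the plan says.** SAP 3.5.1 defines the outcome once per patient for each of five variants: "Proportion of patients with a CompEx event during the 52-weeks following randomisation, for each of CompEx PR, PS,PA, PRS and PRSA". An event is a first occurrence, so a patient contributes a single yes or no per variant.

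SAP 4.2.5.7 says these proportions "will be compared between treatments using a log-binomial regression model". It names one model term ("Treatment group will be included as a factor in the model") and gives the back-transformed effect as "the ratio of proportions, AZD1419 over placebo", with a two-sided 95% interval and p-value. It then says the model is fitted with the SAS "procedure PROC GLIMMIX as described in" SAP 4.2.4.1.

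SAP 4.2.4.1 deals with loss of asthma control at successive clinic visits, with treatment and visit as factors. It carries out the analysis "using a log-binomial regression model using PROC GLIMMIX in SAS with a random subject effect". If convergence fails, it moves to a random intercept with a Laplace approximation, then to fewer covariates. As a last step, "the random statement will be removed which will result in a conventional logistic regression model being fitted".

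Neither section says that the random effect is dropped for CompEx, or how a logistic estimate would be presented there.

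**The concern.** A random subject effect describes correlation between repeated records on the same patient. With one binary record per patient there is no such correlation to estimate. A programmer who follows the cross-reference literally would ask the software for a variance that the data cannot supply. The likely outcomes are a convergence failure or an estimate that depends on where the algorithm stops. A failure leads into the fallback sequence, and that sequence ends on the odds scale, whereas SAP 4.2.5.7 promises a ratio of proportions. For common events the two measures differ substantially. The same wording governs all five CompEx variants.

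**Working it through.** **Plan's own figure.** The documents give no event rate, effect size or power for the CompEx proportion, so there is nothing to reproduce for this analysis. One illustration below borrows the loss-of-control planning rates (SAP 1.3: 20% and 60% still controlled, so 80% and 40% with an event). These rates do reproduce the plan's 32 events. The hazard ratio is ln(0.60)/ln(0.20) = 0.317, and Schoenfeld's formula at two-sided 0.05 and 90% power gives 4 × (1.960 + 1.282)² / (ln 0.317)² ≈ 32. Their use for CompEx is an assumption.

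**Step 1: is the random-effect variance identifiable?** SAP 1.3 gives 81 randomised patients and the protocol (3.5) gives 1:1 allocation, so take about 40 per arm, with 32/40 events on placebo and 16/40 on AZD1419. One record per patient leaves two observed proportions. The model asks for three quantities: an intercept, a treatment effect and a variance. The best attainable log-likelihood is

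32 ln 0.8 + 8 ln 0.2 + 16 ln 0.4 + 24 ln 0.6 = −46.937.

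The exact marginal likelihood reaches this value at random-effect SD 0.01, 0.5, 1 and 2, under both the log and the logit link. It is flat, so the data say nothing about the variance.

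**Step 2: what happens to the treatment effect?**

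- *Log link, unrestricted normal intercept.* The marginal proportion is exp(η + σ²/2). The σ² term is the same in both arms and cancels, so the ratio is 0.50 at every SD. Only the intercept moves: its exponential falls from 0.80 at SD 0.01 to 0.11 at SD 2.
- *Logit link.* The conditional odds ratio moves from 0.167 at SD 0 to 0.151, 0.118 and 0.055 at SD 0.5, 1 and 2, all with the same fit.
- *Log link with the Laplace approximation, linear predictor kept below zero.* This is the approximation named in SAP 4.2.4.1, computed directly rather than run in SAS:

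| Random-effect SD | Approximate log-likelihood | Estimated ratio |
|---|---|---|
| 0 | −46.9 | 0.50 |
| 0.5 | −36.7 | 0.39 |
| 1 | −15.8 | 0.48 |
| 2 | +62.4 | 1.00 |

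The approximate likelihood keeps rising over the values tried and the ratio wanders. A failed or meaningless fit is therefore a realistic prospect.

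**Step 3: size of the scale change at the last fallback.** For event proportions p₀ (placebo) and p₁ (AZD1419), the odds ratio is [p₁/(1 − p₁)] / [p₀/(1 − p₀)]. At 80% v 40% it is (0.4/0.6)/(0.8/0.2) = 0.167. Over a range of assumed placebo rates:

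| Placebo rate | OR if the true ratio is 0.50 | OR if the true ratio is 0.75 |
|---|---|---|
| 20% | 0.44 | 0.71 |
| 40% | 0.375 | 0.64 |
| 60% | 0.29 | 0.55 |
| 80% | 0.17 | 0.375 |

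**Step 4: the simple model on the same data.** Log-binomial regression with treatment only and no random effect gives (16/40)/(32/40) = 0.50, 95% CI 0.33 to 0.75. Logistic regression on the same counts gives an odds ratio of 0.17, 95% CI 0.06 to 0.45.

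**The case against.** The strongest reply is that SAP 4.2.5.7 is self-contained. It states its own model, its one factor and its own effect measure, and the reference to 4.2.4.1 may only point to the SAS procedure. SAP 4.2.4.9, by contrast, explicitly takes over the GEE approach of 4.2.4.1. The fallback sequence there is also triggered by failure of a GEE model, which 4.2.5.7 does not mention. On that reading the model is saturated: the estimate is the ratio of two observed proportions, and no fallback is needed unless an arm has no events or all events. This reading is possible. But the text refers to the fit as described in a section whose description includes the random subject effect and the convergence steps, and nothing excludes them. Two programmers could reasonably implement different models.

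Three further objections limit the point, and all stand:

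- A reader might infer that the treatment ratio itself is not identifiable. It is identified; only the variance component is not. With an unrestricted log link the model ratio does not depend on the variance at all. Ratios that fall with the SD (0.48, 0.41, 0.26 and 0.09 at SD 0.25, 0.5, 1 and 2 for 80% v 40%) appear only if individual probabilities are capped at 1, and the SAP states no cap.
- A reader might infer that the SAP plans to report an odds ratio under the name of a ratio of proportions. It does not say so. That label is attached to the log-binomial estimate, and the SAP is silent on what follows a fallback. Mislabelling is an open risk, not a stated plan.
- CompEx is exploratory. The Cox analysis of time to first CompEx event does not use this model.

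**Conclusion.** The point holds as a specification gap in SAP 4.2.5.7. Taken literally, the cross-reference brings in a random effect whose variance one record per patient cannot identify, and a final fallback that leaves the promised scale without a reporting rule. For an assumed true ratio of 0.50, the fallback odds ratio would look slightly stronger at a 20% placebo event rate (0.44) and about three times stronger at 80% (0.17). A general claim of severalfold exaggeration is not supported, because it needs high event rates and the documents give none for CompEx. The conclusion rests on reading the cross-reference as covering the model description and not only the procedure name. The consequence is confined to the exploratory CompEx proportion analyses, for all five variants; no primary, secondary or safety analysis is affected.

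**What to change.** In SAP 4.2.5.7, replace the reference to 4.2.4.1 with a self-contained statement: for each CompEx variant, fit a log-binomial model with one record per patient, treatment as the only factor and no random effect. Add that, if the fit does not converge, a method that stays on the ratio scale will be used, such as Poisson regression with log link and robust variance.

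The cost is one or two sentences in the SAP and a simpler program than the one now described. No data collection or sample size changes, and the reported measure remains the one the section already promises.
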